# 5 Study Objectives and Purpose

The objective of the study is to evaluate the safety and performance of the enVista trifocal intraocular lens when implanted in the capsular bag.

# 5.1 Study Variables

Inherent to the description and analyses of primary study variables is an assumption that adverse events, including serious adverse events and second surgical interventions, and changes in visual acuity are independent events for the eyes of each enrolled subject.

## 5.1.1 Safety Variables

The primary safety variables will be:

- The incidence of all serious adverse events, including secondary surgical interventions (SSIs) related to the optical properties of the IOL, through Post-Operative Visit 4 (Day 120 to Day 180 after second eye IOL implantation)
- The cumulative rate of secondary surgical interventions due to the optical properties of the lens, through Post-Operative Visit 4 (Day 120 to Day 180 after second eye IOL implantation)
- The incidence of adverse events, through Post-Operative Visit 4 (Day 120 to Day 180 after second eye IOL implantation), compared to ISO Safety and Performance Endpoint (SPE) rates as defined in ISO 11979-7:2018 Annex E

The secondary safety variables will be:

(Data for these safety variables will be summarized with descriptive statistics lacking hypothesis)

- The incidence of subjects experiencing at least one severe visual disturbance, defined as the highest grade of severity or bothersomeness (separately) reported by subjects using the Quality of Vision (QoV) questionnaire through Post-Operative Visit 4 (Day 120 to Day 180 after second eye IOL implantation)
- Photopic contrast sensitivity with glare at Post-Operative Visit 4 (Day 120 to Day 180 after second eye IOL implantation)
- Mesopic contrast sensitivity with glare at Post-Operative Visit 4 (Day 120 to Day 180 after second eye IOL implantation)
- Mesopic contrast sensitivity without glare at Post-Operative Visit 4 (Day 120 to Day 180 after second eye IOL implantation)

### **5.1.2** Performance Variables

The primary performance variables will be:

- Photopic uncorrected distance visual acuity (UDVA) for first implanted eyes at 4 m at Post-Operative Visit 4 (Day 120 to Day 180 after second eye IOL implantation)
- Photopic uncorrected near visual acuity (UNVA) for first implanted eyes at 40 cm at Post-Operative Visit 4 (Day 120 to Day 180 after second eye IOL implantation)
- Photopic uncorrected intermediate visual acuity (UIVA) for first implanted eyes at 66 cm at Post-Operative Visit 4 (Day 120 to Day 180 after second eye IOL implantation)

The secondary performance variables will be:

- IOL rotation for all trifocal eyes at Post-Operative Visit 4 (Day 120 to Day 180 after second eye IOL implantation)
- Change from baseline (preoperative) in uncorrected photopic near visual acuity (UNVA) at 40 cm for first implanted eyes to Post-Operative Visit 4 (Day 120 to Day 180 after second eye IOL implantation)
- Change from baseline (preoperative) in uncorrected photopic intermediate visual acuity (UIVA) at 66 cm for first implanted eyes to Post-Operative Visit 4 (Day 120 to Day 180 after second eye IOL implantation)

The supportive performance variables will be:(Data for these performance variables will be summarized by treatment group with descriptive statistics lacking hypotheses)

- Photopic corrected visual acuity (CDVA, DCNVA, and DCIVA) for first implanted eyes at Post-Operative Visit 4 (Day 120 to Day 180 after second eye IOL implantation)
- Photopic and mesopic binocular uncorrected near and intermediate visual acuity (UNVA and UIVA) at 40 cm and 66 cm, respectively, at Post-Operative Visit 4 (Day 120 to Day 180 after second eye IOL implantation
- Binocular CDVA defocus curves from +1.50 D to -3.50 D

# 5.2 Overall Study Design and Plan: Description

This will be a prospective, multicenter, randomized, masked, controlled, parallel groups, binocular study at up to approximately twelve (12) clinical sites in Canada with 168 subjects undergoing bilateral cataract extraction and IOL implantation of the enVista one-piece hydrophobic acrylic trifocal IOL (model MX60EFH) or the enVista one-piece hydrophobic acrylic monofocal intraocular lens (model MX60E). The enVista MX60E monofocal IOL was selected as the comparator IOL for this study to confirm or refute the enVista MX60EFH trifocal IOL provides improved near and intermediate visual acuity while maintaining distance visual acuity. The use of a comparator IOL made from the same material assures the results will be independent of the chemical composition of the lenses. Visual acuity improvements are key features of the optical design for the MX60EFH trifocal IOL that should distinguish it from the MX60E monofocal IOL.

Subjects scheduled to undergo cataract surgery by phacoemulsification and bilateral implantation of intraocular lenses (IOLs) will be screened for eligibility. Subjects will be

examined preoperatively to obtain a medical history, establish a baseline for ocular condition, and determine eligibility. Both eyes of each subject will be included in the study and must meet eligibility criteria at the Pre-Operative Visit. At the time of determination of eligibility to participate in the study at the Preoperative Visit, subjects will be successively enrolled at a clinical site and randomly assigned by an interactive response technology (IRT) system in a 2:1 ratio to either the enVista MX60EFH trifocal IOL or the enVista MX60E monofocal IOL, respectively. Randomization information will be obtained only by the Investigator or clinic staff not involved in conducting any post-surgical assessment that requires masking. All staff privy to the randomization assignment will sign attesting their commitment to not share randomization information with anyone other than the Investigator.

Postoperatively, subjects will undergo ophthalmic examinations at regular intervals per the study visit schedule. The Investigator or his/her qualified designee will provide standardized pre-, peri-, and postoperative care for all study subjects at his/her clinical site (refer to **Section 9** for additional information). A delegated examiner(s) at each site who is masked to the randomized assignment of each subject will perform postoperative visual acuity testing. Every effort will be made to ensure that postoperative assessments for a subject are completed by the same examiner.

# 5.3 Investigators

The clinical investigation will be conducted at up to approximately twelve (12) investigative sites in Canada.

The clinical investigation will be conducted by Investigators who are determined by the Sponsor to be suitably qualified by medical and clinical training and experience as a licensed ophthalmologist to conduct this study in compliance with all applicable Health Canada (HC) regulations, ISO 14155:2020, and local regulations. In particular, Investigators should be familiar with the risks and benefits described in **Section 10.3** and potential adverse events and adverse device effects that may occur, including and not limited to those described in **Section 10.4.1**. Investigator training and experience will be determined by the Sponsor to be suitable based on the Investigator's medical training and licensure.

Each investigative site will attempt to enroll a minimum of approximately ten to fifteen (10-15) subjects. In the event that selected sites do not meet expected enrollment, the Sponsor may decide to increase enrollment as needed at other currently active sites, and/or replace low enrolling or non-enrolling sites, to satisfy study enrollment requirements. No Investigator shall contribute more than 25% of the total subjects in the investigation as specified in ISO 11979-7:2018.Study

#### 5.4 Study Duration

Eligible subjects who are enrolled in this study will be followed to Post-Operative Visit 4 (Day 120 to Day 180 after second eye IOL implantation).

# 6 Selection and Withdrawal of Subjects

Approximately one hundred sixty-eight (168) subjects (approximately 336 eyes) at up to approximately twelve (12) clinical sites in Canada scheduled to undergo bilateral

phacoemulsification cataract surgery and IOL implantation of the same assigned IOL will be enrolled in this clinical study.

The study purpose, procedures, and subject responsibilities will be explained to the potential participant. The subject's willingness and ability to meet the follow-up requirements will be determined. When it has been established that the subject is willing to participate, written informed consent will be obtained (*cf.* Section 0). To determine eligibility, written informed consent must be obtained from each study subject prior to performing any study specific procedures, those which are not part of the Investigator's routine standard of care. Enrollment will be consecutive enrollment of all eligible subjects. A complete ophthalmic examination will be done at the Preoperative Visit scheduled within 30 days but no less than 5 days before the first eye surgery.

Application of the inclusion and exclusion criteria in the following sections will result in the selection of an investigational population which is approximately representative of the intended target population.

# 6.1 Subject Inclusion Criteria

This study will include subjects who meet the following inclusion criteria:

- 1. Subjects must be 18 years of age or older on the date the Informed Consent Form (ICF) is signed.
- 2. Subjects must have the capability to understand and provide written informed consent on the Institutional Review Board (IRB) / Institutional Ethics Committee (IEC) approved Informed Consent Form (ICF) and authorization as appropriate under local privacy regulations.
- 3. Subjects must have a clinically significant cataract (cortical, nuclear, subcapsular, or combination) in each eye, as determined by the medical judgment of the Investigator, that is considered amenable to treatment with standard phacoemulsification cataract extraction and capsular IOL implantation, with CDVA equal to or worse than 20/40 in at least one eye, with or without a glare source.
- 4. Subjects must have a CDVA projected to be equal to or better than 20/32 after IOL implantation in each eye, as determined by the medical judgment of the Investigator or measured by potential acuity meter (PAM) testing, if necessary.
- 5. Subjects must have clear intraocular media other than the cataract in both eyes.
- 6. Subjects must have discontinued use of contact lenses for at least 2 weeks (for hard or toric lenses) or 3 days (for soft lenses) prior to the pre-operative examination, and throughout the clinical study.
- 7. Contact lens wearers must demonstrate a stable refraction (within ±0.50 D for both sphere and cylinder) in both eyes, as determined by manifest refraction on two consecutive examination dates after discontinuation of contact lens wear.
- 8. Subjects must require an IOL power from +16.0 diopter (D) to +27.0 D in both eyes.

9. Subjects must be willing and able to comply with all treatment and follow-up study visits and procedures, and to undergo second eye surgery within 7-30 days of the first eye surgery.

# 6.2 Subject Exclusion Criteria

This study will exclude subjects (or eyes) who meet any of the following exclusion criteria:

- 1. Subjects who have used an investigational drug or device within 30 days prior to entry into this study and/or will participate in another investigation during the period of study participation.
- 2. Subjects who have any corneal pathology (e.g., significant scarring, guttata, inflammation, edema, dystrophy, etc.) in either eye.
- 3. Subjects who have significant anterior segment pathology that might increase intraoperative risk or compromise IOL stability (e.g., pseudoexfoliation syndrome, synechiae, iris atrophy, traumatic cataract, lens subluxation, traumatic zonulolysis, zonular dialysis, evident zonular weakness or dehiscence, hypermature or brunescent cataract, etc.) in either eye.
- 4. Subjects who have uncontrolled glaucoma in either eye.
- 5. Subjects who have previous retinal detachment or clinically significant retinal pathology involving the macula in either eye.
- 6. Subjects who have proliferative or non-proliferative diabetic retinopathy in either eye.
- 7. Subjects who have a congenital ocular anomaly (e.g., aniridia, congenital cataract) in either eye.
- 8. Subjects with instability of keratometry or biometry measurements.
- 9. Subjects using any systemic or topical drug known to interfere with visual performance, pupil dilation, or iris structure within 30 days of enrollment or during the study (refer to the relevant attachment of the study reference manual).
- 10. Subjects who have current or previous usage of an alpha-1-selective adrenoceptor blocking agent or an antagonist of alpha 1A adrenoceptor (e.g., Flomax® (tamsulosin HCl), Terazosin, or Cardura).
- 11. Subjects who have a history of chronic or recurrent inflammatory eye disease (e.g., iritis, scleritis, iridocyclitis, or rubeosis iridis) in either eye.
- 12. Subjects who have a visual disorder, other than cataracts, that could potentially cause future acuity losses to a level of 20/100 or worse in either eye.
- 13. Subjects who have had previous intraocular or corneal surgery in either eye, with the exception of laser trabeculoplasty.
- 14. Subjects with any active preoperative infectious conjunctivitis, keratitis, or uveitis in either eye.
- 15. Subjects who have a preoperative corneal astigmatism > 1.0 D in either eye as measured by corneal topography or keratometry, irregular astigmatism, or skewed radial axis (note: corneal incisions intended specifically to reduce astigmatism are not allowed during the study).
- 16. Subjects who cannot achieve a minimum pharmacologic pupil dilation of 5.0 mm in both eyes.

- 17. Subjects who may be expected to require a combined or other secondary surgical procedure in either eye.
- 18. Females of childbearing potential (those who are not surgically sterilized or at least 12 months postmenopausal) are excluded from enrollment in the study if they are nursing, lactating, currently pregnant or plan to become pregnant during the study. Females of childbearing potential must be willing to practice effective contraception for the duration of the study.
- 19. Subjects with any other serious ocular pathology or underlying systemic medical condition (e.g., uncontrolled diabetes) or circumstance that, based on the Investigator's judgment, poses a concern for the subjects' safety or could confound the results of the study.
- 20. Subjects with abnormal pupillary dilation dynamics (as determined by the medical judgment of the investigator) or eccentric or ectopic pupils in either eye.

## 6.3 Subject Disposition Criteria

# 6.3.1 Subject Enrollment

The subject is considered enrolled in the study at the time of randomization at the Preoperative Visit and following confirmation on eligibility according to inclusion/exclusion criteria at the Preoperative Visit and again at Visit 00A (Day 0). Randomization should follow the determination the subject has met all inclusion criteria and none of the exclusion criteria.

# 6.3.2 Subject Screen Failures

A subject who fails to meet eligibility criteria or discontinues from the study of their own volition at the only or last pre-operative screening visit before randomization will be considered a screen failure. Subjects will be seen more than once at a screening visit prior to randomization if they are contact lens wearers to ensure they are adhering to inclusion criteria #6 and #7 and have a stable refraction as described in Appendix B, Section 1.1. Subjects (including contact lens wearers) who do not demonstrate a stable refraction prior to randomization will be screen failed and their data will not be entered in the study database.

# **6.3.3** Subject Completion

The subject has completed the study when he/she completes Postoperative Visit 4 (Day 120 to Day 180 after second eye IOL implantation). A subject who has missed visits or is missing study measurements will remain in the study. Subjects who require further follow-up for an adverse event (AE) or adverse device effect (ADE) will be followed according to Section 10.4.5. The same standard of care will be available for subjects who complete the study as for discontinued subjects (see Section 6.3.4) if such additional care is necessary because of the subjects' participation in the clinical investigation and where it differs from that normally expected for the medical condition in question.

# 6.3.4 Subject Discontinuation

A subject may be discontinued prior to the final study visit for any of the following reasons, including but not limited to:

• Investigator's request (e.g., subject non-compliance or medical decision)

- voluntary withdrawal (subject's request)
- death
- lost to follow-up
- study terminated by Sponsor

A subject may also be discontinued during the first cataract surgery who, during the cataract extraction, experience an anterior or posterior capsule tear or rupture, zonular dialysis, significant iris trauma, or other complication that may cause untoward effects in the judgment of the Investigator. Further, a subject may be discontinued during the first cataract surgery who have zonular instability, need for iris manipulation, or capsular fibrosis or other opacity, or inability to have the IOL fixated in the desired position. In such cases, the subject shall be followed until the condition has stabilized.

Prior to discontinuing a subject, every effort should be made to contact the subject, schedule a final study visit, and obtain as much follow-up data as possible. If a final study visit can be successfully scheduled, the procedures to be completed at that visit are the same as those for Form 4 (Day 120 to Day 180 after second eye IOL implantation) with the exception of procedures for defocus curve and contrast sensitivity sub-studies. Adverse events will be followed as described in Section 10.4.5. Subject withdrawals will be documented clearly on the source document and applicable Case Report Forms (CRFs), elements of an electronic data capture (EDC) system.

Notification of subject withdrawals will be made immediately to the Sponsor.

Only subjects who are randomized but did not have the lens inserted into the eye at the first cataract surgery (Visit 00A) may be replaced. Subjects for whom the lens was inserted but not implanted will not be replaced. Subjects who successfully complete Visit 00A and do not successfully implant the assigned IOL at Visit 00B will continue participation for purposes of collecting safety information only for the "B" eye. Visual acuity measurements for a subject who does not implant the assigned IOL at Visit 00B will be only monocular for the "A" eye. A new subject number will be assigned for subject replacements, as long as the total number of treated subjects at the site does not exceed the maximum number specified in Section 5.3. Subjects who are discontinued from the study following treatment will not be replaced.

Discontinued subjects and discontinued subject eyes should be followed outside of the study protocol according to the Investigator's normal standard of care.

#### 6.3.5 Lost to Follow-Up

Subjects who do not return for scheduled Postoperative Visit(s), as defined by the visit window, and cannot be contacted, may be considered lost to follow-up. The investigator will try at least twice to reach the subject by telephone and/or electronic mail and will send a follow-up letter by certified mail before considering the subject lost to follow-up. These actions will be recorded in the source documents and a copy of the follow-up letter maintained in the investigator's file. The date of discontinuation for subjects lost to follow-up will be seven days after the date that the unanswered certified letter was sent.

Efforts shall be made to keep the number of subjects lost to follow-up to a minimum, below 10% of the number of subjects randomized.

#### 7 Treatment Plan

# 7.1 Methods of Assigning Subjects to Treatment Groups

Approximately 168 subjects (336 eyes) will be randomized in a 2:1 ratio to receive the enVista MX60EFH trifocal (Test) IOL or enVista MX60E monofocal (Control) IOL, respectively, in both eyes.

#### 7.1.1 Treatment Allocation

At the time of the Preoperative Visit, subjects will be randomly assigned to either the enVista MX60EFH trifocal IOL or enVista MX60E monofocal IOL in a 2:1 ratio, respectively, based upon a predetermined randomization scheme.

#### 7.1.2 Randomization Method

Subjects will be randomly assigned to receive either the enVista trifocal (Test) IOL bilaterally or the enVista monofocal (Control) IOL bilaterally according to the randomization scheme to be provided.

The IRT system will be utilized for randomization in this study. Randomization will occur following determination of eligibility at the Preoperative Visit, and randomization will be stratified by site such that the ratio of subjects assigned to the Test MX60EFH trifocal IOL or Control MX60E enVista monofocal IOL at each site will be approximately 2:1.

# 7.1.3 Treatment or Subject Replacement

There is no treatment or subject replacement planned for this study other than that described in Section 6.3.4.

## 7.2 Masking/Unmasking

The Investigator implanting the IOL and designated site personnel will be unmasked to the assignment of IOLs. Subjects and designated postoperative evaluator(s) will be masked to the IOLs assigned. Upon completion of study participation, subjects will be notified of the lens identification that they have received.

A qualified masked examiner at each site, who is unaware of which IOL has been implanted for each subject, shall perform post-operative measurements including manifest refraction, visual acuity, contrast sensitivity, and defocus curves. Every attempt should be made to have the same masked examiner perform the same post-operative measurements for an individual subject throughout the subject's study participation.

In an emergency situation where knowledge of the study treatment is critical to subject safety or the study is prematurely terminated, the study treatment for a subject can be unmasked by the unmasked Investigator. Under normal circumstances, masking should not be broken. The Investigator must record the date, time, and reason for unmasking the study treatment in the source documentation. Individual unmasking by the Investigator will normally result in withdrawal of a subject from the study.

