#### 7.4 Protocol Deviations

A deviation from the protocol is an unintended and/or unanticipated departure from the procedures and/or processes approved by the Sponsor and the IRB/IEC and agreed to by the Investigator.

The investigator or designee must document and explain in the subjects' source documentation any deviation from the approved protocol. Protocol waivers will not be allowed under any circumstances, and the Investigators are required to comply with all aspects of the investigational plan. However, the investigator may implement a deviation from, or a change of, the protocol in an emergency situation to protect the rights, safety and well-being of subjects and to eliminate an immediate hazard to study subjects without prior IRB/IEC or Sponsor approval. As soon as possible after such an occurrence, the implemented deviation or change, the reasons for it, and any proposed protocol amendment(s) should be submitted to the IRB/IEC for review and approval, to the Sponsor, and to the regulatory authorities, if required.

The date of, and reason for, deviations in all cases will be documented. Protocol deviations affecting the safety of the subject or the integrity of the study must be reported by the Investigator to the IRB/IEC promptly. Reporting of all other protocol deviations must adhere to the requirements of the governing IRB/IEC.

Protocol assessments will continue for a subject until the end of the study, unless the protocol deviation puts the subject at risk or the subject's condition requires that he/she be discontinued from the study.

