#### 11.4.1.3 ISO Grid Adverse Events

Cumulative and persistent ISO grid AEs will be summarized categorically for all Test group eyes of the Safety Set by treatment. Subjects will be analyzed according to treatment received.

The numerator for each cumulative AE will be the number of all implanted Test group eyes reporting the AE at least once after surgery. The denominator for cumulative AEs will be the number of all implanted Test group eyes.

The numerator for each persistent AE will be the number of all implanted Test group eyes with the event at Visit 4 (Day 120 to Day 180 after second eye IOL implantation). The denominator for persistent AEs will be the number of all implanted Test group eyes present at Visit 4 (Day 120 to Day 180 after second eye IOL implantation).

For each ISO grid AE, a one-sided exact binomial test comparing the proportion of Test group eyes with the AE to the relevant control rate will be completed. If the resulting p-value is less than or equal to 0.05, then the null hypothesis will be rejected. If none of the null hypotheses are rejected, then the test lens will be statistically successful in these endpoints.

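### Section 7.2 makes withdrawal the normal result of individual unmasking, so a safety-related code-break can remove a subject from the persistent-adverse-event tests and the per-protocol UDVA test

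*Combined protocol and SAP*

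**What the plan says.** Section 7.2 (Masking/Unmasking) sets two occasions for individual unmasking: "In an emergency situation where knowledge of the study treatment is critical to subject safety or the study is prematurely terminated". It requires the date, time and reason to be recorded, and then states the consequence: "Individual unmasking by the Investigator will normally result in withdrawal of a subject from the study". The same section says who already knows the lens: "The Investigator implanting the IOL and designated site personnel will be unmasked to the assignment of IOLs". Subjects and the designated postoperative evaluators are the masked parties.

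Section 6.3.4 (Subject Discontinuation) describes what follows. Before discontinuation, "every effort should be made to contact the subject, schedule a final study visit, and obtain as much follow-up data as possible". If that visit can be arranged, "the procedures to be completed at that visit are the same as those for Form 4", apart from the defocus and contrast sensitivity sub-studies. Afterwards, "Discontinued subjects and discontinued subject eyes should be followed outside of the study protocol according to the Investigator's normal standard of care". The section's list of reasons for discontinuation is open-ended and does not mention unmasking.

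The analyses treat such a subject differently:

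- **SAEs, optical SSIs, cumulative ISO events** (11.4.1.1 to 11.4.1.3): all implanted eyes, or the Safety Set, which is every subject with an implanted eye (11.3.2).
- **Persistent ISO events** (11.4.1.3): "The denominator for persistent AEs will be the number of all implanted Test group eyes present at Visit 4". The numerator is likewise events present at Visit 4.
- **UDVA** (11.4.3.1 and 11.4.7): PP Set, no imputation; subjects without all primary acuities measured inside the Visit 4 window are excluded.
- **UNVA and UIVA** (11.4.3.2 and 11.4.3.3): ITT Set with multiple imputation.

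**The concern.** Section 7.2 ties withdrawal to the code-break itself rather than to the subject's condition or consent. Apart from premature termination of the whole study, code-breaks occur in subjects with a safety emergency. Any Visit 4 data lost this way may therefore be related to outcome.

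Two pass/fail analyses depend on the subject being seen at Visit 4. One is the set of persistent ISO adverse-event tests, part of the third primary safety endpoint, where success requires that no null hypothesis be rejected. The other is the UDVA non-inferiority test. For the persistent events the direction is clear: removing an affected Test eye makes rejection less likely, which favours the lens.

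The treatment is an implant, so leaving the study does not in itself end exposure. Elsewhere the protocol leans towards keeping subjects. Section 9.1.3 retains a subject whose second eye is discontinued and goes on recording safety data for that eye. Section 7.4, on deviations, sets a similar default: "Protocol assessments will continue for a subject until the end of the study, unless the protocol deviation puts the subject at risk". A second exception there covers a medical need to leave the study.

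**Working it through.** **1. The plan's own figures (Sections 11.2.1 and 11.2.3).** Inputs: 100 Test and 50 Control subjects, SD 0.15, margin or difference 0.2, one-sided 0.05 for UDVA, two-sided 0.05 for UNVA and UIVA.

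- Standard error = 0.15 × √(1/100 + 1/50) = 0.02598. Noncentrality = 0.2 / 0.02598 = 7.70 on 148 degrees of freedom.
- Power exceeds 0.9999 for all three endpoints, in agreement with the stated value above 99%.
- Enrolment: 100/0.9 = 111.1, rounded up to 112; 50/0.9 = 55.6, rounded up to 56; total 168, as stated.
- With 10 further Test subjects lost (90 and 50), power still exceeds 0.9999. The issue is bias, not power.

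**2. Where the subject goes after withdrawal.** An event recorded before exit remains in the SAE, optical-SSI and cumulative ISO numerators, and the eye remains in their denominators. For UNVA and UIVA the subject stays in the ITT Set with an imputed value. For persistent ISO events, an eye not present at Visit 4 leaves both numerator and denominator. For UDVA, a subject without in-window Visit 4 acuity leaves the PP Set.

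**3. Whether the exit visit repairs this.** Visit 4 is Day 120 to Day 180 after the second surgery. An exit visit held before Day 120 fails the PP window rule, and the plan does not say that it counts as presence at Visit 4 for the persistent-event denominator. Section 10.4.5 has ongoing SAEs followed to outcome, but that does not put the eye into the Visit 4 count. The same section does not require CRF documentation of the follow-up of ongoing AEs after exit.

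**4. Size for the persistent-event tests.** The test is a one-sided exact binomial: reject when P(X ≥ r | n, p₀) ≤ 0.05. Take n = 200 Test eyes, from 100 completing Test subjects. The ISO control rates p₀ are not in the documents, so 0.3%, 0.5% and 1% are assumptions. Start at the smallest count that rejects, then remove one bilaterally implanted subject (n = 198).

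| Assumed p₀ | Critical count, n = 200 | One affected eye lost | Both eyes affected and lost |
|---|---|---|---|
| 0.3% | 3/200, p = 0.023 | 2/198, p = 0.120 | 1/198, p = 0.45 |
| 0.5% | 4/200, p = 0.019 | 3/198, p = 0.078 | 2/198, p = 0.26 |
| 1% | 6/200, p = 0.016 | 5/198, p = 0.04997 | 4/198, p = 0.138 |

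With one affected eye the result changes from fail to pass at 0.3% and 0.5%. At 1% it stays a rejection, though only just. With both eyes affected it changes at all three rates.

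**5. Size for UDVA.** If k of 100 Test subjects are lost and their acuity would have been worse by D logMAR, the Test mean is understated by about (k/100) × D. With D assumed between 0.3 and 1.0, one lost subject gives 0.003 to 0.010 and five give 0.015 to 0.050, against a margin of 0.2.

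**The case against.** A reader might infer that subjects with serious events vanish from the safety data. The documents do not support that: SAE, optical-SSI and cumulative ISO rates keep every implanted eye, and ongoing SAEs are followed to outcome. Only the persistent part of the third primary safety endpoint, and events arising after exit, are exposed.

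A reader might also infer that these subjects have no late acuity at all. Section 6.3.4 asks for a final visit with Form 4 procedures, and two of the three primary acuity endpoints are imputed. That stands, but the visit is best-effort and may fall outside the window.

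It would be too strong to say that withdrawal serves no masking purpose. Subject and evaluator masking matters for acuity and for the Quality of Vision questionnaire. This justifies flagging values obtained after unmasking; it does not require ending data collection.

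Three further points reduce the exposure. The implanting Investigator already knows the lens, so formal code-breaks should be few, and the documents give no expected number. The word *normally* leaves discretion. The reversals in the table need several things at once: a Test subject, a persistent event, an unmasking, a withdrawal, no Visit 4 data, and a count exactly at the critical value. Nothing in Section 7.2 links unmasking to persistent events. For acuity no direction of bias is established, since Control subjects can also be unmasked.

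Nor do the documents establish that the lens always stays in place: Section 11.4.1.2 foresees explantation and replacement, and explantation of the first eye before Visit 4 already excludes the subject from the PP Set. Finally, Section 7.4 is a contrast rather than a contradiction. It defines a deviation as something unintended or unanticipated, and an unmasking permitted by Section 7.2 does not fit that definition.

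**Conclusion.** The point holds in a limited form and is a minor improvement to the plan. Section 7.2 states a rule, not a gap: a code-break for safety normally ends participation, and the resulting loss can be outcome-related in two places, the persistent ISO adverse-event tests and the PP UDVA test. The later course of such subjects may also go unrecorded.

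The effect on UDVA is small against the margin, and power is unaffected. For rare persistent events one subject can be decisive, but only at or near the critical count and depending on control rates that are assumed here. How often this would arise cannot be estimated from the documents; it is probably seldom.

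**What to change.** Replace the withdrawal sentence in Section 7.2 with:

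> Unmasking is documented with date, time and reason; study assessments and data collection continue through Visit 4 unless the subject withdraws consent or is discontinued for another reason listed in Section 6.3.4.

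Add to Section 11.4.3 a sensitivity analysis that omits acuity values measured after unmasking. No change to the ITT or Safety Set definitions is needed, since Sections 11.3.1 and 11.3.2 already include every implanted subject. Unmasking should not be relabelled a deviation, for the reason given above.

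The cost is one sentence and one sensitivity analysis, with no change to sample size. The downside is that a few acuity and questionnaire values will be collected unmasked. They can be identified from the date that Section 7.2 already requires to be recorded.
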